8.4 Follow-up of Adverse Events

All AEs will be followed to adequate resolution or until considered stable.

All SAEs reported to the Virology Research Clinic will be relayed to the Human Subjects Division (HSD) of the University of Washington as required by HSD policy.

9 Data Analysis Plan

Positive response to VZV proteins in lymphoproliferation assays will be determined on a per-cell-line basis surpassing this threshold: at least $2.33 \times$ median absolute deviation of all negative-control antigen samples above the median response of those same samples. This calculation has a theoretical false-positive rate of 1.0%. VZV antigen wells will be scored positive only if both replicates exceed the threshold. ORFs synthesized as fragments (eg, ORF22) were scored positive once if any fragment was deemed positive.

Antibody titers, T-cell frequencies, and T-cell breadth will be compared between the different time points using the nonparametric Friedman's test for repeated measures. If significant, subsequent analysis of measures using Dunn's test identified which time points were different from prevaccine samples. Correlation analyses will be performed using the Spearman's test. Nonparametric tests will be used because the data are likely to be highly left skewed, thus did not satisfy assumptions of normality. Two-sided P values $<.05$ will be considered statistically significant. Statistical tests and graphs were generated using Prism (v7 or greater, GraphPad Software, La Jolla, California).

10 Human Subjects Protections

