The FDA has licensed a live attenuated VZV vaccine to prevent both chickenpox and shingles. The vaccine composition is the same for both indications. The dose varies: the dose for shingles prevention is 14 times higher than the dose for chickenpox prevention. In 1995, universal vaccination with Varivax (the brand name for the pediatric dose) became universally recommended in the US. In 2005, the results of a landmark randomized controlled clinical trial in the US, done in the Veteran's administration system, showed that administration of Zostavax (the brand name for the higher adult dose) lead to a moderate reduction in the incidence of both shingles and PHN when given to older adults. Currently, the Zostavax vaccine is FDA approved for immunocompetent adults 50 or older. ACIP recommends Zostavax at age 60 and most insurance companies follow this guideline by paying for Zostavax at age 60.

It is not clear how Zostavax works. It is generally thought that long term immune memory to VZV, set into place by childhood chickenpox, gradually wanes over time, and that a delicate equilibrium between the latent virus in neurons and the immune system finally tips in favor of the virus and the individual gets clinical shingles. Zostavax, being a live vaccine, is thought to be able to stimulate or re-stimulate a specific immune response to VZV, include the components of antibodies, T-cells with the CD4 marker, and T-cells with the CD8 marker. Because Zostavax contains all 70 proteins encoded by the VZV genome, it is thought that these immune components are stimulated quite broadly and that the vaccine elicits immune responses to many VZV proteins. To date, the research on this topic is simplistic and minimal. Our lab has developed systems to use before and after vaccine blood samples to measure in quantitative detail the CD4 and CD8 T cell immune response to each individual VZV protein.

2 Study Purpose

The overall purpose of this protocol is to study the immune responses to shingles vaccination.

3 Participant Selection

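### The cut-off of median + 2.33 × MAD has the stated 1.0% false-positive rate only if the MAD is scaled by 1.4826, which Section 9 does not say

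*Combined protocol and SAP*

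**What the plan says.** The rule is in the combined protocol and SAP, Section 9 (Data Analysis Plan). Positivity in the lymphoproliferation assays "will be determined on a per-cell-line basis surpassing this threshold": at least 2.33 times the "median absolute deviation of all negative-control antigen samples above the median response of those same samples". The next sentence gives the operating characteristic: "This calculation has a theoretical false-positive rate of 1.0" percent.

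Two further rules come after that sentence:
- Replicates: "VZV antigen wells will be scored positive only if both replicates exceed the threshold".
- Fragments: "ORFs synthesized as fragments (eg, ORF22) were scored positive once if any fragment was deemed positive".

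Section 9 gives no scaling constant for the MAD, no distribution behind the 1.0%, and no number of negative-control samples per cell line.

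Two other places show how the calls are used. The background text before Section 2 says the laboratory can "measure in quantitative detail the CD4 and CD8 T cell immune response to each individual VZV protein". Section 9 lists the outcomes: "Antibody titers, T-cell frequencies, and T-cell breadth will be compared between the different time points".

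**The concern.** A multiplier of 2.33 goes with a 1% upper tail when it multiplies a standard deviation. Here it multiplies a MAD, which in normal data is about two thirds of a standard deviation. Without a constant to convert one to the other, the printed cut-off is lower than the one to which the 1.0% belongs.

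This is the only positivity rule in the analysis plan, and it decides which VZV proteins count as recognised. An analyst who takes the text literally and one who assumes the conventional scaling could make different calls on weak responses from the same data. A reader would also take 1.0% as the assay's nominal error rate, whichever version was run.

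The consequence is confined to individual ORF calls and the absolute level of breadth. The Friedman comparison across visits keeps its type I error, provided one rule is used at every visit and the negative controls are comparable in number and distribution across visits.

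**Working it through.** **Inputs.** From Section 9: multiplier 2.33, spread measure MAD, one-sided (above the median), stated rate 1.0%. Assumed, because the plan does not say: normal control responses and, to begin with, enough controls that the median and MAD are known without error.

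**1. Reproducing the 1.0%.** Treat 2.33 as a multiple of the SD: 1 − Φ(2.33) = 0.0099, which rounds to 1.0%. This needs the MAD to be rescaled to estimate the SD. The factor is 1/Φ⁻¹(0.75) = 1/0.6745 = 1.4826, and the margin becomes 2.33 × 1.4826 = 3.45 raw MADs.

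**2. The rule as printed.** The raw MAD is 0.6745 SD, so the margin is 2.33 × 0.6745 = 1.5716 SD. The rate is 1 − Φ(1.5716) = 0.0580, or 5.8%, per replicate.

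**3. How far the cut-offs differ.** With the control median at m control SDs above zero, the scaled-to-raw ratio is (m + 2.33)/(m + 1.5716). For assumed m = 0, 1, 3 and 10 this is 1.48, 1.29, 1.17 and 1.07. The margin above the median always differs by 1.48.

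**4. Does the both-replicates rule explain the 1.0%?** The probability that both replicates exceed the threshold (bivariate normal, many controls) depends on their correlation, which the plan does not give:

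| Replicate correlation | Raw MAD | Scaled MAD |
|---|---|---|
| 0 | 0.34% | 0.01% |
| 0.25 | 0.79% | 0.04% |
| 0.5 | 1.5% | 0.13% |
| 0.8 | 3.0% | 0.37% |
| upper bound | 5.8% | 0.99% |

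The raw-MAD figure equals 1.0% only at a correlation of about 0.34.

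**5. Finite controls.** The median and MAD are estimated within each cell line. Mean single-replicate rates from simulated normal controls (control counts assumed):

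| Controls | Raw MAD | Scaled MAD |
|---|---|---|
| 10 | 11.3% | 5.1% |
| 20 | 8.6% | 2.9% |
| 50 | 7.0% | 1.7% |
| 100 | 6.4% | 1.3% |
| 200 | 6.1% | 1.2% |

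With both replicates required, independent noise and 10, 20 or 50 controls, the rates are 2.5%, 1.2% and 0.65% (raw) and 0.84%, 0.24% and 0.06% (scaled).

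**6. Effect on detection.** Take a true response a given number of control SDs above the control median, with the same spread and many controls. The probability that both replicates exceed the cut-off is:

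| Response (assumed) | Replicate correlation | Raw MAD | Scaled MAD |
|---|---|---|---|
| 3 SD | 0 | 85% | 56% |
| 3 SD | 0.8 | 89% | 67% |
| 4 SD | 0 | 98% | 91% |

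**The case against.** The strongest reply is that this is a missing constant and not an analysis error. The pair 2.33 and 1.0% fits a scaled MAD, so the stated rate itself tells an informed reader which scaling was meant, and nothing in the plan shows that the laboratory uses the raw MAD. If it already scales, no call changes. This stands as the likelier reading. It does not make the text correct, because the term names the unscaled quantity and a literal reader would compute a different cut-off.

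A second reply is that 5.8% overstates the practical error, since a well is scored positive only if both replicates exceed the cut-off. It is true that 5.8% must not be read as the well-level rate; with the raw MAD and many controls that rate lies between 0.34% (independent replicates) and 5.8%. But the 1.0% is attached to the threshold calculation, before the replicate rule appears, and matching it through that rule needs a particular correlation that the plan does not give.

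A third reply is that scaling does not secure 1.0% either. This also stands. With few controls the scaled rule exceeds 1.0% per replicate, and Section 9 itself expects skewed data. Adding the constant brings the formula and the nominal rate into agreement; it does not guarantee the realised rate. That is the reason to state the conditions beside the figure.

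**Conclusion.** The concern holds. Followed as printed, the threshold has a theoretical single-replicate false-positive rate of 5.8%, about 5.9 times the 0.99% of the scaled version (5.80/0.99). Both figures assume normal control responses and many controls, and both precede the replicate and fragment rules. The documents cannot settle whether the laboratory's calculation is affected or only its description. It is worth correcting because individual protein calls and absolute breadth depend on this cut-off.

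**What to change.** First establish which MAD the laboratory's calculation uses.

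- **Default:** write the threshold in Section 9 as the negative-control median + 2.33 × 1.4826 × MAD (= median + 3.45 × MAD). The formula then agrees with the stated nominal 1.0%.
- **Only if the laboratory uses the unscaled MAD and wants to keep that cut-off:** say that the MAD is unscaled and restate the rate as 5.8%.
- **In either case:** label the rate as theoretical, per replicate, under normality and with many controls, before the both-replicates and any-fragment rules.

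The text change is one or two sentences. If the laboratory already scales, the default changes no call; the alternative must not be used then, because it would lower the cut-off and change calls. If the laboratory uses the raw MAD, the alternative changes no call but reports a less favourable rate. In that case the default would mean re-scoring every visit with one rule and losing some weak responses, on the scale shown in step 6 of the working.

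### The 1.0% false-positive rate in Section 9 holds per well and only with a scaled MAD; it is not the rate of an ORF call, which depends on the replicate and fragment rules

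*Combined protocol and SAP*

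**What the plan says.** All the scoring rules are in Section 9, Data Analysis Plan.

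- Threshold: positivity "will be determined on a per-cell-line basis surpassing this threshold", namely "at least $2.33 \times$ median absolute deviation of all negative-control antigen samples above the median response of those same samples". The text does not say whether the MAD is raw or rescaled to estimate a standard deviation.
- Error rate: "This calculation has a theoretical false-positive rate of 1.0"%. The figure is attached to the threshold calculation.
- Replicates: "VZV antigen wells will be scored positive only if both replicates exceed the threshold".
- Fragments: "ORFs synthesized as fragments (eg, ORF22) were scored positive once if any fragment was deemed positive".
- Use: "Antibody titers, T-cell frequencies, and T-cell breadth will be compared between the different time points using the nonparametric Friedman's test for repeated measures".

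The plan gives no false-positive rate for an antigen scored in duplicate, for an ORF or for breadth. It does not give the number of fragments per ORF, how many ORFs are fragmented, or the number of negative-control wells.

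**The concern.** The 1.0% is the only operating characteristic that the plan gives for calling a response positive, and it raises two problems.

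First, 2.33 is the normal multiplier for a 1% upper tail when the unit is a standard deviation. A raw MAD is about two thirds of a standard deviation, so the threshold as written is lower than the stated rate implies. This affects every ORF.

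Second, the analysis does not use single wells. It uses ORF calls and their count, breadth. Requiring two replicates moves the error rate down. Accepting any one of several fragments moves it up, but only for ORFs made in pieces. A protein could then look more often recognised because of how it was synthesised. That matters for any protein-by-protein description; the background section says that the laboratory's systems can "measure in quantitative detail the CD4 and CD8 T cell immune response to each individual VZV protein".

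**Working it through.** **Inputs from the documents.** Multiplier 2.33, stated rate 1.0%, two replicates that must both pass, and the any-fragment rule (all Section 9). There are 70 VZV proteins (background section: "Because Zostavax contains all 70 proteins encoded by the VZV genome"); I assume that all are tested.

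**Assumptions, because the documents give no figure.** Normal background; k = 2, 3 or 5 fragments; replicate correlation 0 to 1; fragment correlation 0 to 0.8; 1 or 10 fragmented ORFs. Unless stated otherwise, the control median and MAD are treated as known without error.

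**Step 1: the plan's own figure.** With the MAD scaled by 1.4826, the threshold is 2.33 SD, and 1 − Φ(2.33) = 0.0099, or 1.0%. The figure reproduces.

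**Step 2: the threshold as written.** For normal data the MAD is 0.6745 SD. So 2.33 × 0.6745 = 1.57 SD, and 1 − Φ(1.57) = 0.058, or 5.8% per well.

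**Step 3: both replicates.** If p is the per-well rate and replicates are independent, the rate is p²: 0.0099² = 0.01% (scaled) and 0.058² = 0.34% (raw). If replicates are fully correlated it stays at p: 1.0% and 5.8%.

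**Step 4: any of k fragments.** If q is the rate per construct after Step 3 and fragments are independent, the ORF rate is 1 − (1 − q)^k.

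| MAD | Replicates | k = 1 | k = 2 | k = 3 | k = 5 |
|---|---|---|---|---|---|
| Scaled | independent | 0.01% | 0.02% | 0.03% | 0.05% |
| Scaled | correlation 0.8 | 0.38% | 0.75% | 1.13% | 1.87% |
| Scaled | fully correlated | 1.0% | 2.0% | 3.0% | 4.9% |
| Raw | independent | 0.34% | 0.67% | 1.0% | 1.7% |
| Raw | fully correlated | 5.8% | 11.3% | 16.4% | 25.8% |

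The scaled rows take the per-well rate as exactly 1%.

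**Step 5: correlated fragments.** By simulation at a 1% base, the ratio to a single construct for k = 2, 3 and 5 is 1.9, 2.7 and 4.0 at fragment correlation 0.5, and 1.6, 2.1 and 2.8 at 0.8. So k is a ceiling on the ratio.

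**Step 6: breadth.** At 1% per fragment with independent fragments, the expected number of false-positive ORFs is 70 × 0.01 = 0.70 if none is fragmented. With one fragmented ORF it is 69 × 0.01 + 0.0199 = 0.71 (k = 2) to 69 × 0.01 + 0.0490 = 0.74 (k = 5). With ten it is 0.80 to 1.09. At 0.01% per fragment, all these figures are about one hundredth as large.

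**Step 7: estimated threshold.** When the median and MAD are estimated from few control wells, the per-well rate rises even with scaling. Simulation gives 6.2% with 8 wells, 2.1% with 32 and 1.5% with 64.

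**The case against.** The strongest reply is that the plan contains no false statement about ORFs. The 1.0% is tied to the threshold, and the replicate and fragment rules come after it. A reader might infer that 1.0% is offered as the protein-level or breadth rate; the text does not say so. That reply stands for the fragment rule. It does not answer the scaling point, because the 1.0% fails for the threshold itself if the MAD is raw. Scaling may be intended, but the text does not say so.

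A reader might also infer that fragmented ORFs have k times the error rate and so exceed 1.0%. The documents do not support this. They give no k, the factor k needs fragments that err independently, and the replicate rule may leave even a five-fragment ORF at 0.05%.

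A third inference is that the comparison of breadth across visits is compromised. It is not, on this ground: the same rule applies at every visit, so it does not by itself inflate the type I error of the Friedman test. Nor does Section 9 plan a test of one ORF against another, and Section 2 states the purpose only as studying immune responses to the vaccination. The per-protein wording describes what the laboratory can do. Counting a fragmented protein once is also sensible in itself.

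What remains is that fragmented ORFs have more chances of a false call, unless their fragments err in complete lockstep, and the plan neither adjusts for this nor reports it.

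**Conclusion.** The concern holds in two parts of unequal weight.

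The main part is the threshold. As written, it does not give the stated 1.0% under a normal background. The per-well rate is 5.8% with the raw MAD and 1.0% only after scaling by 1.4826. This rests on normality and on enough control wells to fix the median and MAD. Section 9 itself expects skewed data, although it does not say that this covers the control wells, so 1.0% should be read as nominal.

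The lesser part is that 1.0% is not the rate of an ORF call. For a single construct the rate runs from 0.01% to 1.0% (scaled) or 0.34% to 5.8% (raw), depending on replicate correlation. For a fragmented ORF it is higher by a factor of at most about k. The direction is certain unless fragments are perfectly correlated, but the size is not known, because k and the correlations are not given. The consequence lies mainly in per-ORF description. Absolute breadth changes little if few ORFs are fragmented.

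**What to change.** In Section 9:

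1. Define the threshold as median + 2.33 × 1.4826 × MAD of the negative controls, so that the nominal 1.0% holds per well under a normal background. State the number of negative-control wells per cell line.
2. Describe 1.0% as a per-well figure, before the replicate and fragment rules.
3. List the number of fragments for each ORF and report the ORF-level false-positive rate after both rules. Give it as a range over replicate and fragment correlation, or estimate it from negative-control wells where there are enough. Rates of 0.01% to 1% cannot be estimated from a handful of wells.
4. Keep the any-fragment rule as primary. As a sensitivity analysis, show breadth and per-ORF positivity with a fragment-adjusted threshold, using a per-fragment rate of 1 − (1 − q)^(1/k). On the scaled-MAD scale, for independent to fully correlated replicates, the multiplier is about 2.46 to 2.58 for k = 2, 2.53 to 2.72 for k = 3 and 2.62 to 2.88 for k = 5. These values assume independent fragments and overcorrect if fragments are correlated, which is why they should not be primary.

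The cost is some wording and a rescoring script, with no new samples. If the raw MAD would otherwise have been used, fewer weak responses will be called positive. The sensitivity analysis also loses some sensitivity for fragmented ORFs.

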4.2 Enrollment Visit (Day 0)

Eligible subjects will return for an Enrollment Visit. A blood sample (up to 110 ml) will be obtained for immunological assays and VZV research serology. Additional blood (up to 10 ml) will be obtained for HLA typing. After the blood sample is obtained, a standard dose of Zostavax will be administered. Participants will be provided with a copy of the CDC Shingles Vaccine Information Sheet.

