4.3 Follow-up Visits

Participants will return for follow-up visits at Day 7-14, 28, and 180. Blood will be drawn for immunological assays and VZV research serology.

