5.1 Potential Risks

Phlebotomy: Blood drawing may cause discomfort and/or bruising. Rarely an infection may develop. Clinical discretion will be used when drawing blood from elderly (65+) participants. If necessary, blood draw volumes will be adjusted (50 ml minimum).

Zostavax vaccination: Mild reactions include redness, soreness, swelling, or itching at the site of the injection and headache. Serious adverse reactions include anaphylaxis. There is no documentation of a person getting chickenpox from someone who has received the shingles vaccine. Some people who get the shingles vaccine will develop a chickenpox-like rash near the place where they were vaccinated. There is a risk of disseminated infection in immunocompromised persons; therefore, they will be excluded from the study. There is a risk of transmission of the vaccine virus between vaccines and susceptible contacts. As with any vaccination, there may be side effects that are not known at this time.

Biopsy: The diameter of the biopsy will be equivalent to a very small straw. Anticipation of the procedure may cause anxiety. The biopsy itself may cause pain, even with the use of an anesthetic. Biopsies may cause a pressure or tugging sensation. Bleeding may also occur; in the case of excessive bleeding, silver nitrate will be applied. Infection and scarring are rare complications of biopsies. Biopsies will not be performed on face or neck.

Lidocaine (injectable, +/- epinephrine): Lidocaine administration is associated with temporary pain and burning. Skin biopsy may cause discomfort even when the area of the skin is numbed using lidocaine. Allergic reactions to lidocaine may occur, even in subjects with no history of allergic reactions. Examples of allergic reactions include wheezing or difficulty in breathing, lightheadedness or fainting, skin rash and itching. As with any drug there may be unknown side effects.

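### The Friedman and Dunn tests use only participants with all four samples, so someone who misses Day 180 is also lost from the Day 28 versus Day 0 comparison

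*Combined protocol and SAP*

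**What the plan says.** Section 9 (Data Analysis Plan) sets out one route for comparing visits: antibody titers, T-cell frequencies and T-cell breadth are to be "compared between the different time points using the nonparametric Friedman's test for repeated measures". The contrasts follow from it: "If significant, subsequent analysis of measures using Dunn's test identified which time points were different from prevaccine samples". The significance level is two-sided 0.05. Correlations are handled separately: "Correlation analyses will be performed using the Spearman's test".

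There are four scheduled samples. Section 4.2 places the baseline draw before vaccination: "After the blood sample is obtained, a standard dose of Zostavax will be administered". Section 4.3 adds three more: "Participants will return for follow-up visits at Day 7-14, 28, and 180". Appendix A shows the same four.

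The documents define no analysis set. They give no rule for a missed visit or a failed assay, no imputation, no rank method for incomplete data and no separate paired test for the early visits. Section 4.5 allows additional visits when the laboratory needs more blood, but does not describe them as replacing a scheduled visit. Blood drawn later could not restore a missed Day 7-14 or Day 28 value in any case.

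**The concern.** Friedman's test ranks each participant's values across all the time points, so it is defined only for participants who have all of them. Dunn's follow-up works from the same rank sums and inherits the same participants. Someone who gives blood at Day 0, Day 7-14 and Day 28 but not at Day 180 therefore adds nothing to the early contrasts, although both samples for each of those contrasts are in hand.

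Two things are at stake. The first is precision: paired data already collected from vaccinated people go unused. The second is interpretation: the early responses become responses among people who also supplied a Day 180 value, so an early result is conditioned on a later event. Day 180 comes 180 - 28 = 152 days after the preceding visit, so some loss there is plausible. A value can also be missing when the visit is attended. Section 5.1 allows the draw to be cut to 50 ml in participants aged 65 or over, against up to 110 ml in Section 4.2, and a smaller draw might not cover every assay.

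**Working it through.** The plan states no sample size, power or dropout figure, so there is none to reproduce. The check covers the mechanism first and then its size.

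**Inputs from the documents.** Time points k = 4 (Sections 4.2 and 4.3, Appendix A). Friedman's test, then Dunn's test against prevaccine, two-sided 0.05 (Section 9).

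**Assumed inputs.** A miss rate m at each of the three follow-up visits, independent between visits, with Day 0 always present. As an alternative, loss d at Day 180 only.

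**1. Mechanism.** Each complete participant contributes ranks 1 to 4. Dunn's contrast is the difference between two rank sums, with standard error sqrt(n·k(k+1)/6) = sqrt(n·20/6), where n counts complete participants only. In simulated data on 10 participants with Day 180 missing for 2, Friedman's statistic could not be computed on all 10. Omitting missing values gave chi-square 12.75, p = 0.0052. Running the test on the 8 complete participants alone gave the same values. The other two participants' first three samples had no effect.

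**2. Loss spread over the three follow-up visits.** The share usable by Friedman and Dunn is (1-m)^3. The share with a given Day 0/visit pair is 1-m. The fraction of available pairs discarded is 1 - (1-m)^3/(1-m) = 1 - (1-m)^2.

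| m | Complete at all four | Have the Day 0/Day 28 pair | Available pairs discarded |
|---|---|---|---|
| 5% | 85.7% | 95% | 9.8% |
| 10% | 72.9% | 90% | 19.0% |
| 15% | 61.4% | 85% | 27.8% |
| 20% | 51.2% | 80% | 36.0% |

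For an assumed 20 enrolled and m = 10%: 20 × 0.729 = 14.6 participants used, against 20 × 0.90 = 18.0 with the pair.

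**3. Loss at Day 180 only.** The early contrasts could use 100% of participants, and the planned method uses 1-d: 90% at d = 10%, 80% at d = 20%. For the same statistic, the standard error of an early contrast rises by sqrt(1/(1-d)). At d = 20% this is sqrt(1/0.8) = 1.118, about 12%.

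**The case against.** The mechanism is hard to dispute, but there is a fair case for limiting what is drawn from it.

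- **Scope.** A reader might infer that a participant with a missing value drops out of the whole analysis. The documents do not support that. Spearman correlations need only the pairs they use. The loss is also per endpoint: a failed T-cell assay does not remove that person's complete antibody titers. Section 9 does not say outright that all four visits enter one test. Four is the natural reading, but not a stated rule.
- **Bias.** A reader might infer that the early results will be biased because older or sicker people stop attending. Nothing in the documents says who stops attending, and Section 3.2 excludes immunosuppressed people and those judged unable to meet the protocol's requirements. The conditioning on Day 180 is real; the direction and size of any bias cannot be derived.
- **Size.** The larger losses in the table need independent misses at every visit. With full attendance the loss is zero.
- **The gain from changing.** The 12% figure assumes an unchanged statistic, whereas Dunn's test cannot use the incomplete participants and must be replaced. A simulation assumed 200 enrolled, 20% lost at Day 180 only, independent normal errors, a Day 28 shift of 0.3 SD and unadjusted 0.05. Day 28 power was about 0.64 for Dunn on completers, 0.75 for Dunn had nobody been lost, and 0.83 for a signed-rank test on all pairs. Part of the gain therefore comes from the different test.
- **Importance.** The stated purpose is descriptive, and no primary endpoint or efficacy claim rests on this test. A fixed set of participants also makes visits directly comparable, so restricting to completers has some rationale.

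All of this narrows the point. None of it supplies a missing-data rule or a test that uses the available pairs.

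**Conclusion.** The concern holds for the Friedman and Dunn time-point comparisons, separately for each endpoint. On the natural reading of Section 9, one missing value among the four visits removes a participant from that endpoint's overall test and from all three contrasts with prevaccine, including early contrasts for which both samples exist. The defect is the combination of a complete-block method with silence on missing data.

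The size rests wholly on assumed attrition. At 10% the comparison is 73% against 90% if loss is independent at each follow-up visit, and 90% against 100% if it falls only at Day 180. The documents support neither a claim that a particular number of participants will be lost nor a claim that the early results will be biased. The change is still worth making: it is inexpensive, and without it the handling of missing values is left to software defaults or to a choice made after the data are seen.

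**What to change.** In Section 9:

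1. State that each contrast with Day 0 (Day 7-14, Day 28, Day 180) uses every vaccinated participant who has both samples for that endpoint.
2. Replace Dunn's test with a paired Wilcoxon signed-rank test, with Holm adjustment across the three contrasts within each endpoint. Unlike a within-participant rank test, the signed-rank test depends on the measurement scale and on roughly symmetric differences. State the scale for each endpoint, and how zero differences are handled.
3. If an overall test is kept, use an incomplete-block version such as Skillings-Mack, and say whether it still decides if the contrasts are run.
4. Report n for each contrast.
5. Give the Friedman and Dunn result in four-visit completers as a sensitivity analysis.

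**Cost.** This changes analysis wording and code only: no extra visits, blood or participants. Skillings-Mack may need a routine outside the named package. The contrasts may rest on slightly different participants, which the reported n makes visible.

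**Limit.** This stops the early contrasts depending on Day 180 attendance. It does not correct the Day 180 contrast if the people lost by then respond differently, and neither the signed-rank test nor Skillings-Mack adjusts for that.
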